### **Homogeneity of treatment effect**

To assess the homogeneity of the treatment effect on the primary endpoint across the levels of PIFR subgroups, the same ANCOVA model as in the primary analysis will be fitted in the overall population but replacing the treatment term by a treatment-by-PIFR subgroup term. A descriptive p-value of treatment effect homogeneity at week 4 will be calculated. No overall treatment effect will be estimated from this model as it is not interpretable. The analysis will be done separately for population before and after COVID-19.

Similarly, the same ANCOVA model as in the primary analysis will be fitted in the overall population but replacing the treatment term by a treatment-by-continuous baseline PIFR term. A descriptive p-value of treatment effect homogeneity at week 4 will be calculated. No overall treatment effect will be estimated from this model as it is not interpretable. The analysis will be done separately for population before and after COVID-19.

The results of the analysis of the primary endpoints for tiotropium + olodaterol FDC within the optimal and sub-optimal PIFR groups will be presented in a forest plot and the treatment by PIFR subgroup interaction p-value will be provided. Sensitivity analysis will be performed by including additional covariates such as severity, gender and age in the model to adjust for potential differences in prognostic factors between sub-optimal and optimal PIFR subgroups.

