1.4.3 Discussion

Tiotropium + olodaterol FDC delivered via the Respimat® device was shown to be effective in improving lung function, quality of life and dyspnea as well as improve exercise tolerance. It has also shown to be safe and well tolerated over 1 year in a moderate to very severe COPD population; however, there is currently no clinical data available from randomized controlled trials or from real world studies to demonstrate whether COPD patients can benefit from tiotropium + olodaterol Respimat® independently of the inspiratory flow they can generate.

Data from this study will provide this evidence and therefore help in the personalization of treatment selection for COPD patients. Considering a placebo arm is included in the study, the treatment and follow-up period has been kept short, and includes a clinic visit after two weeks of treatment to assess the patients' condition. Further measures are in place to minimize the risk for the study population are the exclusion of the most severe COPD population, the population treated with inhaled corticosteroids, those patients with a very recent COPD exacerbation, or with a history of frequent COPD exacerbations and at risk of COPD exacerbations.

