#### 7.4.1 Primary analysis of the primary endpoint(s)

The primary endpoint will be analyzed using an ANCOVA model including the fixed, categorical effect of treatment and the fixed continuous effect of baseline. The data is collected at baseline (visit 2) and at visit 4.

Significance tests will be based on adjusted means using a two-sided  $\alpha = 0.05$  (two-sided 95% confidence intervals).

The primary analysis will be performed on the FAS within the optimal and sub-optimal PIFR groups, respectively. Patients will be analyzed according to the PIFR stratum to which they belong (regardless of any miss-assignment to treatment based on identification of the wrong stratum), as such an error occurs before randomization and is therefore consistent with regulatory guidance.

The Kenward-Roger approximation will be used to estimate denominator degrees of freedom and adjust standard errors. Significance tests will be based on least-squares means using a two-sided  $\alpha = 0.05$  (two-sided 95% confidence intervals).

The following SAS code will be used for the analysis.

```
PROC MIXED DATA=alldat method=reml order=formatted;
  CLASS trtp (ref=last);
  MODEL chg = base trtp ;
  LSMEANS trtp / cl diff om cov;
RUN;
```

Here the endpoint is chg (change from baseline), baseline value of the endpoint is base and the treatment group is trtp. The data set alldat will be set to the optimal and sub-optimal PIFR subgroups, respectively. The data set should only include post baseline visits since change from baseline will be identical to zero for the baseline visit.

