#### 7.5.1.1 Primary analysis of the key secondary endpoint(s)

The key secondary endpoint will be analyzed using the restricted maximum likelihood (REML) based approach using a mixed model with repeated measurements (MMRM). The analysis will be performed on the FAS within the optimal and sub optimal PIFR groups, respectively. The data is collected at baseline (visit 2), visit 3 and visit 4.

The analysis will include the fixed, categorical effect of treatment at each visit and the fixed continuous effect of baseline at each visit. Visits will be treated as repeated measures with an unstructured covariance structure used to model the within-patient measurements.

The Kenward-Roger approximation will be used to estimate denominator degrees of freedom and adjust standard errors. Significance tests will be based on least-squares means using a two-sided  $\alpha = 0.05$  (two-sided 95% confidence intervals).

If a patient misses a visit, the missing data will not be imputed. The mixed effect model will handle missing data based on a likelihood method under the “missing at random” assumption.

The following SAS code will be used for the analysis.

```
PROC MIXED DATA=alldat cl method=reml order=formatted;
  CLASS usubjid trtp (ref=last) tptno;
  MODEL chg = trtp*tptno base*tptno / ddfm=kr solution;
  REPEATED tptno / subject=usubjid type=un r rcorr;
  LSMEANS tptno*trtp / pdiff=all om cl alpha=0.05 slice=tptno;
  RUN;
```

Here tptno is the planned analysis day number for each visit, the endpoint is chg, baseline value of the endpoint is base and the treatment group is trtp.

The data set alldat will be set to the optimal and sub-optimal PIFR subgroups, respectively. The data set should only include post baseline visits since change from baseline will be identical to zero for the baseline visit.

In the event of non-convergence, the following methods will be attempted (in order) to overcome it:

1. Add the ‘singular=1e-10’ option in the model statement – This raises the threshold at which columns are declared linearly dependent (from typically 1e-12).
2. Set ‘maxiter=100’ in the PROC MIXED statement – This increases the number of convergence iterations used from a default of 50.
3. Set ‘scoring=4’ to specify use of the Fisher scoring algorithm in the first 4 iterations.
4. Include the statement ‘performance nothread’ – this removes multi-threading from the calculations.

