##### **Homogeneity of treatment effect**

To assess the homogeneity of the treatment effect on the key secondary endpoint across the levels of PIFR subgroups, the same MMRM model as in the key secondary analysis will be fitted in the overall population but replacing the treatment term by a treatment-by-PIFR subgroup term. A descriptive p-value of treatment effect homogeneity at week 4 will be calculated. No overall treatment effect will be estimated from this model as it is not interpretable. The analysis will be done separately for population before and after COVID-19.

Similarly, the same MMRM model as in the key secondary analysis will be fitted in the overall population but replacing the treatment term by a treatment-by-continuous baseline PIFR term. A descriptive p-value of treatment effect homogeneity at week 4 will be calculated. No overall treatment effect will be estimated from this model as it is not interpretable. The analysis will be done separately for population before and after COVID-19.

The results of the analysis of the key secondary endpoints for tiotropium + olodaterol FDC within the optimal and sub-optimal PIFR groups will be presented in a forest plot and the treatment by PIFR subgroup interaction p-value will be provided. Sensitivity analysis will be performed by including additional covariates such as severity, gender and age in the model to adjust for potential differences in prognostic factors between sub-optimal and optimal PIFR subgroups.

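### The continuous-PIFR homogeneity model drops the treatment main effect, so its p-value mainly tests whether the drug works, not whether the benefit varies with PIFR

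*SAP*

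**What the plan says.** The primary model in SAP 7.4.1 has two terms besides the intercept: "MODEL chg = base trtp", with treatment as a class variable. For homogeneity, SAP 7.4.2 modifies this model twice. The first version swaps treatment for treatment-by-PIFR-subgroup. The second is "fitted in the overall population but replacing the treatment term by a treatment-by-continuous baseline PIFR term". Protocol 7.3.1 says the same.

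For trough FEV1, SAP 7.5.1.2 applies the same replacement to the mixed model whose statement in SAP 7.5.1.1 is "MODEL chg = trtp*tptno base*tptno / ddfm=kr solution".

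Each version yields a descriptive p-value for homogeneity at week 4. Neither document gives code for the continuous-PIFR model, names the contrast, restores a treatment main effect or sets an origin for PIFR. For the subgroup version only, the plan adds that "the treatment by PIFR subgroup interaction p-value will be provided". The SAP, but not the protocol, also states: "The analysis will be done separately for population before and after COVID-19".

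**The concern.** The replacement is harmless for the two-level subgroup. Treatment-by-subgroup terms give four cell means, and the interaction is a contrast among them. It does not carry over to a continuous variable. Taking treatment out of the primary model and putting treatment-by-PIFR in leaves one intercept, the baseline covariate and one PIFR slope per arm. The two arms are tied together at PIFR = 0, a value no patient has, and the fitted benefit is the slope difference multiplied by PIFR. A drug that helps everyone equally must then produce different slopes.

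In the mixed model, the treatment-by-visit term also carries the visit intercepts. Replacing it leaves a single intercept for both arms and both visits.

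Protocol 1.4.3 gives as the evidence gap whether patients benefit "independently of the inspiratory flow they can generate", and Protocol 1.3 makes the same case. This is the only analysis visible in the documents that treats PIFR as a continuous measure and not as a cut at 60 L/min. Coded as written, it would tend to contradict the hoped-for finding exactly when that finding is true.

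**Working it through.** **Inputs from the documents (Protocol 7.5 and 7.6).** SD 210 mL; benefit 260 mL for FEV1 AUC0-3h and 140 mL for trough FEV1; N = 200, 1:1, 50 per arm per stratum; two-sided 0.05.

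**Assumptions.** The documents give no PIFR mean or SD, only the 60 L/min cut-off. I used a normal distribution (mean 60, SD 17) or a uniform one (30 to 100), with further runs at means 50 to 75 and SDs 10 to 25 L/min. There is no missing data, and PIFR has no prognostic effect.

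**Plan's own figure.** For 140 mL, SD 210 mL and 90% power, the normal approximation gives 2 × (1.960 + 1.282)² × (210/140)² = 47.3, so 48 per arm, or 96 in total. The exact t-test gives 98 in total with 90.4% power, which matches Protocol 7.6.

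**Closed form.** Write P for PIFR and t = 0/1 for treatment. The model as written is chg = a + baseline + b0·P·(1−t) + b1·P·t. Under 1:1 allocation the slope difference b1 − b0 is the coefficient of P·(t − ½), which is uncorrelated with the intercept and with P. For a constant benefit δ:

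- expected slope difference = δ·E[P] / E[P²]
- SE = 2σ / √(N·E[P²]) (lack of fit adds a little residual variance, which the simulations include)

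Normal PIFR: E[P²] = 60² + 17² = 3889.
- 260 mL: slope difference 260 × 60/3889 = 4.01 mL per L/min; SE = 420/√(200 × 3889) = 0.476; ratio 8.42.
- 140 mL: 2.16/0.476 = 4.54.

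Uniform PIFR: E[P] = 65, E[P²] = 65² + 70²/12 = 4633.
- 260 mL: 3.65/0.436 = 8.36.
- 140 mL: 1.96/0.436 = 4.50.

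Rejection probability is about Φ(ratio − 1.96): essentially 100% at 260 mL and about 99.5% at 140 mL, although the true slope difference is zero.

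**Simulation (2,000 to 3,000 trials per scenario), share with p < 0.05 on the slope-difference or interaction test:**

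| Truth | As written | Main effects kept |
|---|---|---|
| Constant 260 mL, N = 200 | 100% | 4.4–5.8% |
| Constant 140 mL, N = 200 | 99.2–99.6% | 4.3–6.0% |
| No drug effect, N = 200 | 4.7–5.0% | 5.0–5.2% |
| Constant 260 mL, N = 100 | 100% | 5.8% |
| Constant 140 mL, N = 100 | 88% | 4.4% |
| Zero average benefit, true slope 4 mL per L/min | 7% | 50% |

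The third row shows that the false rejections come from the overall drug effect. The last row shows that the model can also miss real dependence.

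**Direction.** Let the true benefit fall with PIFR as 440 − 3P mL: 320 mL at 40 L/min and 200 mL at 80. With normal PIFR, the expected fitted slope difference is 440 × 60/3889 − 3 = 3.79 mL per L/min, which is positive. In simulation the model as written reports a significant rise in 100% of trials.

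**Origin of PIFR.** With PIFR measured from 30 L/min, false rejection is 97–100%. Measured from 60 it is 3–12%, and mean-centred about 2–4%. Centring is no remedy, because the fitted benefit is then forced to zero at the centre.

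**Which term matters.** With treatment as a class variable, the two slopes already contain a PIFR effect. Adding PIFR without treatment still rejects in 100% (260 mL) and about 99% (140 mL) of trials. The missing treatment term does the damage.

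**Mixed model.** Constant 140 mL, visit correlation 0.5 to 0.8 (assumed), the treatment-by-PIFR term taken by visit but a single intercept: 99.2–99.6% at week 4, against 4.8–5.6% with all terms by visit.

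**Subgroup version.** With a constant benefit, the 1-df difference-in-differences contrast rejects in 4.8–6.0% of trials. The 3-df test of the combined term would reject in 98–100%, because it includes the drug effect itself.

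**The case against.** The strongest reply is that the sentence is shorthand. It reuses the wording of the subgroup version, where it is correct, and a competent programmer might fit the full interaction model anyway. The remark that no overall effect will be estimated would fit that model too. This is possible, but no text or code supports it. The SAP prints code for its primary, mixed-model and imputation analyses and none for this one, so literal programming is a real risk.

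Several narrower points stand:

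- A PIFR slope is already implicit when treatment is a class variable, so only the missing treatment term is harmful.
- The mixed-model percentages rest on reading the PIFR term as by visit, which SAP 7.5.1.2 does not say, although it promises a week-4 result.
- If only the COVID-19 period fits are run, the trough figure falls to about 88% with 100 patients. The AUC figure stays at 100%. The period sizes are not in the documents.
- The 3-df subgroup test is one the plan never names, and the promised interaction p-value largely covers that gap.
- The p-value is descriptive and outside the testing hierarchy. The valid subgroup interaction and forest plot would sit beside it and could expose a spurious result.

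These points limit the consequences. They do not make the stated model a test of homogeneity.

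**Conclusion.** The concern holds. Followed literally with PIFR in L/min, the continuous-PIFR analysis would report PIFR-dependence in about 99–100% of trials when the benefit is constant at the plan's own assumed effects, where 5% is intended. For an effective drug the spurious trend points to more benefit at higher PIFR, and it can do so even when the true trend is the reverse.

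The percentages depend on assumed PIFR distributions, but the result hardly moves across means of 50 to 75 and SDs of 10 to 25 L/min. It does depend on PIFR being uncentred, which is the only reading the documents support. The four confirmatory tests and their type I error are untouched. This should be fixed because it bears on the trial's stated rationale, but it does not threaten the primary conclusions.

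**What to change.** In Protocol 7.3.1 and SAP 7.4.2, state the continuous model as chg = baseline + treatment + PIFR + treatment × PIFR. Take the homogeneity p-value from the 1-df interaction term and report its estimate with a 95% CI, for example per 20 L/min. In SAP 7.5.1.2, use the same terms each by visit, with a visit effect, and take the interaction at week 4. Add the code for both.

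Leave the subgroup model as it is, and state that its homogeneity p-value is the 1-df difference-in-differences contrast, that is, the interaction p-value already promised.

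State that the fit in the whole full analysis set is reported as well as any fits by COVID-19 period. Even with 200 patients, the corrected test finds a true slope difference of 4 mL per L/min in only about half of trials (PIFR SD 15 assumed), so period-specific fits alone would tell the reader little.

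The cost is a few words and one model statement per endpoint. No data, design feature or confirmatory test changes.

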The Respimat® Soft Mist™ Inhaler actively delivers a metered dose of medication, with minimal inspiratory effort from the patient, as a fine slow moving, long lasting mist, with a high fine particle fraction, resulting in a high lung deposition and lower oropharyngeal deposition ([P12-01215](#), [P05-10480](#), [P06-10775](#)). In vitro data has demonstrated that Respimat® Soft Mist™ delivers high lung deposition at low modelled flow rates and across disease severities, and requires only a very low inspiratory effort ([P17-06338](#)).

Dry powder inhalers have higher internal resistance than that of SMIs and pMDIs; as a result, the inspiratory force necessary to overcome the internal resistance of DPIs, to optimally

release the medication from the inhaler and deliver into the airways, is greater than what is required for pMDIs and SMIs. The [REDACTED] has been introduced as a simple, low cost method of measuring an individual's inspiratory flow rate. It is generally accepted that a PIFR of 60 L/Min (optimal PIFR) is required for adequate drug delivery by a DPI with medium internal resistance. In previous studies of small cohorts, approximately 30-50% of patients are unable to generate the targeted PIFR of 60 L/Min as measured by [REDACTED] with medium or low resistance. There is also evidence demonstrating that, at the time of discharge from an acute care hospital for treatment of a COPD-related hospitalization, one third of patients had a sub-optimal PIFR with medium or low resistance measured by [REDACTED]. It has been demonstrated that sub-optimal PIFR is a predictor of 90-day readmission for COPD, days to all-cause readmissions and days to COPD readmission. Multivariate analysis has demonstrated that age, gender, height, forced vital capacity (FVC) % predicted and inspiratory capacity (IC) % predicted are independent predictors of sub-optimal PIFR. This evidence highlights the importance of inspiratory flow rate in the effective delivery of inhaled therapies; yet, the evidence for the benefits provided by currently available inhaled treatments for COPD according to the inspiratory flow rates generated by patients, is scarce.

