7.5 RANDOMIZATION

Approximately 200 patients will be randomized in blocks to double-blind treatment stratified by PIFR optimal and sub-optimal subgroups. Approximately equal numbers of patients will be randomized to each treatment group (50 in tiotropium + olodaterol Respimat® and 50 in placebo Respimat® for each PIFR subgroup). BI will arrange for the randomization and the packaging and labelling of trial medication. The randomization list will be generated using a validated system, which involves a pseudo-random number generator so that the resulting treatment will be both reproducible and non-predictable. The block size will be documented in the Clinical Trial Report. Access to the codes will be controlled and documented.

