##### Missing data analysis

The ANCOVA primary analysis only accounts for missing observations under the MCAR (missing completely at random) assumption. The robustness of the primary analysis to the

MAR (missing at random) assumption will therefore be assessed by performing a multiple imputation (MI) sensitivity analysis with an extended covariate set. Data from Trough FEV1 will also be included in the imputation procedure as it is measured at both visits 3 and 4. It therefore may provide information about patient state prior to discontinuation that is not available directly for the primary endpoint and hence reduce any biases caused by missing data.

Missing data will be multiply imputed 100 times using the MCMC (Markov Chain Monte Carlo) method. The imputation will be performed separately for each combination of treatment and PIFR subgroup. Separate chains will be used for each imputation, with 1000 burn-in iterations. Jeffrey's prior will be used. The seed number will be set to 123795. The following variables will be included in the multiple imputation model: treatment (Tio+Olo vs placebo), continuous baseline FEV1, continuous age, gender (male or female) and disease severity (GOLD group 2 or 3), smoking (yes/no), previous exacerbation (yes/no), country (US, Germany), change from baseline Trough FEV1 at visit 3 and 4 and change from baseline FEV1 AUC0-3h at visit 4.

For each imputed complete data set, the primary endpoint will be analyzed at visit 4 using the primary ANCOVA analysis model. The 100 estimates and standard errors will then be combined using Rubin's rules (16,17) to produce a single estimate with standard error, confidence interval and nominal p-value.

The following SAS code will be used for multiple imputation step.

```
PROC MI data=midat seed=123795 n impute=100 out=miout;
  VAR var;
  MCMC chain=multiple nbiter=1000 prior=jeffreys;
  BY pifr trtp;
RUN;
```

Here the data set is midat, var are all the variables to be entered into model, trtp is the treatment group and pifr is the PIFR sub group. The data set midat must have one record per patient with all variables for each visit arranged horizontally. The variable chg4 is the change from baseline for the endpoint of interest to be analyzed below.

An ANCOVA model will be used on the result of the imputations using the SAS code as follows.

```
PROC SORT data=miout;
  BY _imputation_ pifr;
RUN;
```

```
ODS OUTPUT diff= mixdiff ;
ODS LISTING CLOSE;
```

```

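### Does the covariate-adjusted homogeneity analysis need a fixed formula and treatment-by-covariate terms?

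*SAP*

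**What the plan says.** Protocol 7.3.1 and SAP 7.4.2 (Homogeneity of treatment effect) fit a pooled ANCOVA in which a treatment-by-PIFR-subgroup term takes the place of treatment. A second version works by "replacing the treatment term by a treatment-by-continuous baseline PIFR term". Each gives a descriptive p-value at week 4. The SAP adds, for both: "The analysis will be done separately for population before and after COVID-19".

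After the forest plot and the interaction p-value comes the sentence at issue, a sensitivity analysis with added covariates such as "severity, gender and age in the model to adjust for potential differences in prognostic factors between sub-optimal and optimal PIFR subgroups". SAP 7.5.1.2 repeats it for trough FEV1 with the MMRM. No MODEL statement accompanies it.

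Three other places matter:
- SAP 7.4.2 and 7.5.1.2, Sensitivity analysis: covariate models with the same three factors, run separately in each PIFR subgroup, with GOLD stage as the example of severity.
- Protocol 7.5: patients are "randomized in blocks to double-blind treatment stratified by PIFR optimal and sub-optimal subgroups".
- Protocol 1.1: "age, gender, height, forced vital capacity (FVC) % predicted and inspiratory capacity (IC) % predicted are independent predictors of sub-optimal PIFR".

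**The concern.** The two PIFR strata will probably differ in age and sex, because the protocol itself names both as predictors of sub-optimal PIFR. If the treatment effect also varied with one of these factors, the two strata would show different effects even if inspiratory flow had no influence. A reader might expect the covariate-adjusted homogeneity analysis to deal with this.

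Entered as main effects, the covariates cannot do so. Treatment is randomised within stratum, so the adjustment leaves the expected interaction unchanged whether or not patient mix is driving it. A report that the interaction was unchanged after adjustment for severity, gender and age could then give false reassurance on the trial's central theme, benefit regardless of inspiratory ability. With no formula and an open list, the analysis could also be run in more than one way after the data are seen.

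**Working it through.** **1. The plan's own figures.** Protocol 7.6 gives SD 210 mL, two-sided alpha 0.05, a difference of 140 mL in trough FEV1 and 98 patients per stratum for 90% power. The two-sample t-test gives 98 and 90.4% power (the normal approximation gives 96). All eight sample sizes in Table 7.6: 1 reproduce.

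**2. Precision of the interaction.** With 49 patients per arm in each stratum, the difference between two treatment effects has

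SE = 210 × √(4/49) = 60.0 mL, and a 95% half-width of 1.96 × 60.0 = 117.6 mL.

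**3. What covariate mix does.** Suppose PIFR has no effect, and a binary covariate changes the treatment effect by g mL and has prevalence p in each stratum. Each within-stratum estimate then has expectation (common effect + g·p), so the contrast is

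g × (p_sub-optimal − p_optimal).

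In absolute size: 120 × (0.70 − 0.30) = 48 mL; 80 × 0.40 = 32 mL; 40 × 0.40 = 16 mL; 120 × (0.60 − 0.40) = 24 mL. If g = 0, it is zero for any mix. Covariate main effects do not enter this expression, because treatment is independent of the covariates within each stratum.

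**4. Simulation.** Categorical PIFR, 98 per stratum, residual SD 205 mL, 20,000 trials per scenario, true PIFR effect zero. The mixes and modification sizes are assumptions. Mean contrast, sub-optimal minus optimal, in mL:

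| Scenario (women, sub-optimal vs optimal) | Unadjusted | Main effects | With treatment-by-covariate terms |
|---|---|---|---|
| No modifier | 0 | 0 | 0 |
| 40 mL by sex, 70% vs 30% | −16 | −16 | 0 |
| 80 mL by sex, 70% vs 30% | −33 | −33 | 0 |
| 120 mL by sex, 70% vs 30% | −49 | −49 | 0 |
| 120 mL by sex, 60% vs 40% | −24 | −24 | 1 |
| Smaller modification by all three | −46 | −47 | 0 |

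A separate simulation (50 per cell, SD 210 mL, 4,000 trials) let severity be the modifier: severe disease in 60% vs 30%, with a 100 mL smaller effect. It gave −29, −30 and 0 mL. The algebra holds. Every value in the table is below one standard error (59 to 61 mL).

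**5. What the extra terms would cost and tell.** They widen the SE of the contrast from 60.6 to 63.4 mL (about 5%) up to 59.0 to 67.7 mL (15%) under moderate imbalance. Under strong imbalance it rises to 75.9 mL (26 to 29%).

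The diagnostic would be the change from the unadjusted to the fully adjusted estimate. With 120 mL modification its mean and SD are 48 and 37 mL (70% vs 30%), or 24 and 29 mL (60% vs 40%). With no modifier and 70% vs 30%, its SD is 34.6 mL. Since 48/34.6 = 1.39, it exceeds 48 mL in either direction in about 16% of trials by chance. If COVID-19 split the trial into equal halves, the SE before any added term would be about 210 × √(4/24.5) = 85 mL.

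**6. Which model is meant.** A within-stratum reading would duplicate the models already assigned under Sensitivity analysis. The sentence stands under Homogeneity, follows the interaction p-value and concerns differences between the subgroups, so it points to the pooled model. Adding covariates to a model ordinarily means main effects. The multiple-imputation text in SAP 7.4.2 codes all three: age continuous, gender in two categories, severity as GOLD 2 or 3. What stays open is whether further covariates join, and whether the categorical or the continuous pooled model (or both) is adjusted.

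**7. Continuous PIFR.** No figures are given here for adjusting that model. Read literally, its wording drops the treatment main effect. The contrast between arm-specific slopes then absorbs the treatment effect: about 38 to 39 mL per 10 L/min when PIFR has no influence and the drug effect is 260 mL. How that base model is parameterised is a separate question from covariate adjustment.

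**The case for a change.** The best case for a change runs as follows. Within-stratum effects are already unbiased, so prognostic differences between strata matter only when the effects are compared, and main effects cannot correct that comparison. Stated aim and likely tool therefore do not match. The SAP exists to give more technical detail than the protocol, yet here it repeats the protocol's sentence, while it prints code for the primary, imputation and MMRM analyses. Mix can also hide a difference. With an assumed true PIFR effect of −60 mL and an opposing severity modification of 150 mL (70% vs 30% severe), the contrast averages +1 mL unadjusted, +2 mL with main effects and −59 mL with treatment-by-covariate terms. The covariates are already coded, so the added work is small.

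The algebra stands, as does the observation that the list is open. The mismatch is weaker than it looks. The text speaks of prognostic factors, not effect modifiers, and nowhere says that a stable interaction excludes patient mix. Any error would arise in how a result is reported. The masking example shows that the extra terms can matter when modification is large, but the documents give no evidence of modification of any size: Protocol 1.1 names age and gender as predictors of PIFR, and does not name severity. Even the richer model would not isolate inspiratory flow, since height, FVC % predicted and IC % predicted stay outside it.

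**Conclusion.** No change follows. The missing formula is a gap in a descriptive analysis that an analyst can fill from the surrounding text: severity, gender and age as main effects in the pooled model, coded as elsewhere in SAP 7.4.2. That delivers the prognostic adjustment the plan claims. It does not test whether patient mix explains a difference or a similarity between strata, and an unchanged interaction should not be reported as though it did.

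Adding treatment-by-covariate terms is a matter of judgement, not a clear gain. It would remove an assumed distortion of about 16 to 49 mL, always less than one standard error. The price is an interval about 5 to 15% wider (up to 29% under strong imbalance), and the resulting shift in one trial could rarely be told from chance. The four hypotheses in Protocol 7.2 are tested within stratum, so type I error, power and the confirmatory conclusions are unaffected.

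The sizes rest on assumed covariate mixes and assumed effect modification, for which the documents give no values. That main effects leave the expected contrast unchanged rests only on randomisation within PIFR strata.
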